6.1. Statistical Definitions and Algorithms

6.1.1. Baseline

For all effectiveness and safety endpoints (for which a Baseline data is applicable), Baseline is defined as the last non-missing measurement preceding the initial treatment for subjects assigned to RHA [REDACTED] and randomization date/time for subjects assigned to control groups. For the No-treatment control group, a new Baseline will be defined as the last non-missing measurement at or before Visit 5 (12 weeks after randomization) before continuing to Phase 1b. This new Baseline will be used when applicable for secondary effectiveness analysis.

If the subject is eligible, the BLE's assessment will be used for the Baseline of the primary

endpoint.

If the time of an assessment done the day of initial treatment is missing, the assessment will be considered performed as per protocol to define timing comparing to the treatment.

6.1.2. Multiple Comparisons

Not applicable, there is no multiple comparison in the study.

6.1.4. Analysis Visit Windows

Statistical analyses will be based on scheduled visit as collected in the eCRF without further realignment.

6.1.6. Derived Variables

The following derived and computed variables have been initially identified as important for the analysis of effectiveness.

It is expected that additional variables will be required. The SAP will not be amended for additional variables that are not related to the primary or secondary target variables. Any additional derived or computed variables will be identified and documented in the SAS programs that create the

analysis files. If the SAP is not amended, further derivations related to primary and secondary target variables will be described in the CSR.

6.1.6.1. Responder Rate

Definition of responder: a subject with an absolute ≥ 1 -grade improvement in both eyes on the TIOHS as assessed by the BLE from before initial treatment (Baseline) to 12 weeks after the initial treatment (Visit 5). A negative change from the Baseline value is considered as an improvement.

6.1.6.2. FACE-Q Scores

For FACE-Q “Appraisal of lower eyelids” domain, the outcome of all the question, described below, will be pooled and data will be transformed so that higher scores reflected superior (positive) outcome and adapted to a scale of 100 units (i.e., worst/lowest score = 0, best/highest score = 100). Transformation of scores will be done according to FACE-Q manual.

The Rasch converted scores will be calculated based on the following domain and questions.

Domain “Appraisal of lower eyelids”:

- a. Excess fat under your eyes?
- b. Excess skin under your eyes?
- c. Puffiness under your eyes?
- d. How noticeable the lines under your eyes are?
- e. Crepey (wrinkled) skin under your eyes?
- f. How old the area under your eyes makes you look?
- g. How tired the area under your eyes makes you look?

Raw score will be derived as follow:

- Not at all: 4
- A little: 3
- Moderately: 2
- Extremely: 1

The converted raw scores for items that make up a scale are added to provide a total score. The total score is converted to a score from 0 to 100. If missing data is less than 50% of the scale’s items, insert the mean of the completed items to calculate the total score and round it to the nearest integer.

[REDACTED]

[REDACTED]

AD-ST-33.06 Effective date: 12-Nov-2020

6.1.6.3. Adverse Device Effect

An ADE is any AE with a relationship to the study procedure or study device recorded in the eCRF as 'Possibly related' or 'Probably related' or 'Causal relationship'. An AE with missing or not assessable relationship will be considered as 'treatment related (probably related)'. AEs will be tabulated by all relationship categories recorded in eCRF.

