2.2.2. Safety Endpoints

The safety endpoints of this study include the following:

- Adverse events (AEs), with a focus on treatment related AEs based on the TI assessment, and AEs reported from the Common Treatment Response (CTR) diary, from randomization

Post-injection CTR,

Each AE will be coded to a Preferred Term (PT) and associated System Organ Class (SOC) according to an established and validated adverse reaction dictionary (Medical Dictionary for Regulatory Activities [MedDRA], latest available version) before the randomized treatment code is broken.

3. Overall Study Design and Plan

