Phase 1a: Up to 12 weeks after the initial treatment for the RHA█ group or after randomization for the No-treatment control group; primary endpoint

Subjects who will be randomly assigned to the RHA [REDACTED] group at Screening [REDACTED] [REDACTED] will receive their injection at Visit 1. The TI or designee will call subjects 72 hours post-treatment (Visit 1 Call). Subjects will come to the site [REDACTED] [REDACTED] 12 weeks (Visit 5, primary endpoint) after the initial treatment. Afterwards, subjects will proceed directly to Phase 2. Phase 1b is not applicable for subjects randomly assigned to the RHA [REDACTED] group.

Subjects randomly assigned to the No-treatment control group at Screening will receive

no treatment in Phase 1a of the study. They will come to the site [REDACTED] [REDACTED] 12 weeks (Visit 5, primary endpoint) after randomization. After completing all assessments for Visit 5, subjects will immediately begin Phase 1b (Visit 1b is on the same day as Visit 5) and will receive their initial treatment with RHA [REDACTED].

[REDACTED]

Phase 1b: after the primary endpoint assessment up to 12 weeks after the initial treatment for the No-treatment control group

Phase 1b is only applicable to subjects initially randomly assigned to the No-treatment control group. Once all evaluations applicable for Visit 5 are completed, subjects will proceed directly to Visit 1b (on the same day). Evaluations completed at Visit 5 will be used for Visit 1b and will become the new Baseline for Phase 1b.

Subjects will receive their initial treatment with RHA [REDACTED] at Visit 1b.

Subjects will follow the same schedule as those initially randomly assigned to the RHA® 1 group: RHA® 1 will be administered on the same day (Visit 1b). The TI or designee will call the subject 72 hours post-treatment (Visit 1b Call). Subjects will come to the site [REDACTED] [REDACTED] 12 weeks (Visit 5b) after their initial treatment. Afterwards, subjects will proceed to Phase 2.

Phase 2 and Exit visit: 12 weeks after the initial treatment up to the end of the study for the RHA [REDACTED] group and the No-treatment control group

Phase 2 will occur 12 weeks after receiving initial treatment with RHA [REDACTED] for subjects in the RHA [REDACTED] and the No-treatment control group (after Phase 1b).

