4.2.3. Data Monitoring Committee

Not applicable.

5. Analysis Populations

The following 4 analysis populations are planned for this investigation:

- **Screening population:** All subjects who provide informed consent and demographic and/or Baseline Screening assessment results, regardless of their randomization and treatment status in the investigation. The untreated control group will only be included in the Screening population as they will not receive RHA█ treatment throughout the clinical study.
- **Safety population (SAFT):** All subjects who are assigned to either the RHA█ group or the No-treatment control group and complete Visit 1 █. Subjects will be

analyzed according to their actual arm received.

- **Intent-to-Treat population (ITT):** All subjects who are randomly assigned to either the RHA [REDACTED] or the No-treatment control group and complete Visit 1. Subjects will be analyzed according to their initial arm assignment regardless of whether or not they received RHA [REDACTED].
- **Per Protocol population (PP):** All subjects in the ITT population who completed up to Visit 5 (primary endpoint visit at 12 weeks) with no major CIP deviations that could affect effectiveness assessments. The sponsor will identify major CIP deviations per Protocol Deviation Guidance Plan (PDGP) prior to the database lock.

[REDACTED]

[REDACTED]

[REDACTED]

[REDACTED]

[REDACTED]

[REDACTED]

6. General Issues for Statistical Analysis

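### The rule that turns a missing causality assessment into a related event has no exposure condition, so it can create adverse device effects in controls before they are injected

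*SAP*

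**What the plan says.** SAP section 6.1.6.3 defines the ADE by causality alone: "An ADE is any AE with a relationship to the study procedure or study device recorded in the eCRF as 'Possibly related", or one of the two stronger categories. It then deals with incomplete causality: "An AE with missing or not assessable relationship will be considered as 'treatment related (probably related". It closes with: "AEs will be tabulated by all relationship categories recorded in eCRF".

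Four other places decide whom this rule reaches:

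- Section 2.2.2 makes the safety endpoint "Adverse events (AEs), with a focus on treatment related AEs based on the TI assessment", together with "AEs reported from the Common Treatment Response (CTR) diary, from randomization".
- Section 3.1 gives controls "no treatment in Phase 1a of the study". Their first injection is at Visit 1b, on the same day as Visit 5, 12 weeks after randomization.
- Section 5 defines the Safety population as "All subjects who are assigned to either the RHA█ group or the No-treatment control group and complete Visit 1". It does not require an injection.
- Section 9 runs every safety analysis on that population. Section 9.1 computes AE and ADE incidence over the subjects in each treatment group, with exact 95% confidence intervals.

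**The concern.** Counting an unknown causality as related is a sound convention when the subject has received the product, because any error goes against the product. In a subject who has not been injected the error goes the other way. It adds events to the comparator and brings the two descriptive ADE rates closer together.

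Treatment-related AEs are the stated focus of the safety endpoint. Even one false entry would be awkward to explain: the ADE table would show an event probably related to treatment in a subject who had not yet been treated.

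**Working it through.** **Does the text reach uninjected controls?**

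1. A missing or not-assessable relationship becomes *probably related* (6.1.6.3).
2. *Probably related* is one of the three categories that make an AE an ADE (6.1.6.3).
3. AEs count from randomization, not from first injection (2.2.2).
4. Controls are uninjected from randomization to Visit 1b, that is, for 12 weeks (3.1).
5. Controls who complete Visit 1 belong to the Safety population, and all safety analyses use it (sections 5 and 9).
6. No visible sentence in 6.1.6.3 or 9.1 takes pre-injection events out of the rule.

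The visible text therefore does reach them. The group that section 5 places in the Screening population only is called the untreated control group and is described as never receiving the device. The No-treatment control group does receive it at Visit 1b and is named in the Safety population, so that sentence does not remove it.

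**How large could the effect be?** The SAP gives no figure on this point, so there is nothing to reproduce. What follows is for scale only.

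- Controls: 258 subjects (section 3.3) randomized 3:1 (section 3.1) give 258 / 4 = 64.5, taken as 65.
- One recoded control subject: 1/65 = 1.5% (exact 95% CI 0.04 to 8.3%). Two: 2/65 = 3.1% (0.4 to 10.7%). Three: 3/65 = 4.6% (1.0 to 12.9%).
- Assumptions, not in the SAP: a share *a* of controls has an AE in the 12 untreated weeks, and a share *m* of those lacks a usable relationship. The expected number of false ADE subjects is 65 × *a* × *m*. The chance of at least one is 1 − (1 − *a* × *m*)^65.

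| *a* | *m* | Expected false ADE subjects | Chance of at least one |
|---|---|---|---|
| 5% | 1% | 65 × 0.0005 = 0.03 | 3% |
| 10% | 5% | 65 × 0.005 = 0.33 | 28% |
| 20% | 5% | 65 × 0.010 = 0.65 | 48% |
| 30% | 10% | 65 × 0.030 = 1.95 | 86% |

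**With the rule limited to exposed time**, the recode could create no control ADE before Visit 1b. If the investigator recorded no such AE as related, the rate would be 0/65 = 0.0% (exact 95% CI 0 to 5.5%).

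**The case against.** The best defence has five parts.

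- **The assessor knows the allocation.** Section 3.6 leaves the treating investigator unblinded, and section 9.1 has the investigator judge relationship to procedure and to device. For a subject known to be uninjected, the investigator can simply record the event as unrelated. This stands. A reader might infer that blank entries will pile up in controls, but nothing in the SAP says so. If 20% of controls had an AE (13 of 65), an ADE rate of 5% to 20% (3/65 to 13/65) would need about a quarter to all of those AEs to lack a relationship. The document gives no support for missingness on that scale.
- **The true control rate need not be zero.** The ADE definition covers the study procedure as well as the device, and the visible text does not define the procedure. A control could in principle have a genuine procedure-related AE. This also stands: the error lies in the recoded events, not in every control ADE.
- **No visible decision rests on it.** The visible part of section 9.1 is descriptive, with no between-arm test or threshold. The visible pooling statement, in section 8.3, concerns secondary effectiveness. A reader might infer a distorted formal comparison or a contaminated pooled ADE count, but the visible text plans neither.
- **Safeguards exist.** The tabulation by recorded category and the individual AE listings would expose a recoded entry. They would not take it out of the ADE incidence.
- **The text is incomplete.** Much of section 9.1 is redacted and could present events by phase or exposure. That limits certainty, but the visible rule in 6.1.6.3 still carries no such condition.

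One could also read the ADE definition, which refers to what the eCRF records, as excluding a recoded event. The recode would then have no evident purpose in the section where it stands.

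**Conclusion.** The point holds as a defect of wording with a probably small numerical effect. As visibly written, section 6.1.6.3 counts a control AE before Visit 1b with missing or not-assessable relationship as a probably related ADE, and in that arm it works against its own conservative purpose. Each affected subject adds about 1.5 percentage points to the control ADE incidence. Under the assumed ranges, about 0.03 to 2 such subjects are expected. That rests on about 65 controls, on assumed AE and missingness rates, and on no redacted text already restricting the rule. It is not evidence that the control ADE rate will be materially inflated or that a safety conclusion would change.

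**What to change.** Amend section 6.1.6.3 as follows:

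- Apply the recode only to AEs with onset on or after the subject's first injection (Visit 1 for the RHA group, Visit 1b for controls), or whose onset cannot be shown to precede it. The second clause is needed because section 6.1.7 leaves onset missing when the year is unknown and sets some partial dates to the injection date.
- Leave every relationship recorded by the treating investigator unchanged, including any recorded for an uninjected control. The endpoint is based on that assessment.
- Report control AEs before Visit 1b with missing or not-assessable relationship as such. List them and do not count them as ADEs.

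If a redacted part of section 9.1 already restricts the rule, a cross-reference from 6.1.6.3 is enough.

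The cost is a few lines of SAP text and one date condition in the ADE flag. The rule stays as it is for events after injection.

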6.1.6.4. CTRs

A CTR is a predefined known clinical sign or symptom occurring during the 30 days after injection and reported by the subject for each of the 30 days.

AD-ST-33.06 Effective date: 12-Nov-2020

6.1.6.5. Prior and Concomitant Medications

Medications that started prior to the initial treatment for subjects assigned to RHA [REDACTED] and randomization date/time for subjects assigned to control groups will be considered prior medications.

A concomitant medication is defined as any medication that was administered during the treatment period. This includes medications that started before the treatment period and continued while on treatment and medications that started during the treatment period. [REDACTED]

If the start/stop dates of medication are partially or completely missing, then the medication will be assumed to be concomitant if it cannot be definitely shown that it was not administered during the treatment period. Missing dates will not be replaced.

6.1.7. Data Adjustments/Handling/Conventions

All collected data will be presented in listings. According to this plan, data not subject to analysis will not appear in any tables or graphs but will be included only in the data listings.

All *P* values will be displayed in four decimals and rounded using standard scientific notation (e.g., 0.XXXX). If a *P* value less than 0.0001 occurs, it will be shown in tables as < 0.0001.

For missing AEs onset dates, the convention for replacing missing dates for the purposes of calculating derived variables is as follows:

For partial AE start dates:

- If the year is unknown, then do not impute the date but assign a missing value.
- If the month and day are unknown, then:
 - If the year matches the year of injection date, and the end date (if present) is after injection date, then impute as the month and day of the injection date.
 - Otherwise, assign January.
- If the month only is unknown, then:
 - If the year matches the year of injection date and day is on or after day of injection, then assign the month of injection. If this produces a date after the AE end date, assign the month before.

- If the year matches the year of injection date and day is before day of injection, then assign the month after injection. If this produces a date after the AE end date, assign the month of injection.
- Otherwise, assign January.
- If the day is unknown, then:
 - If the month and year match the month and year of the injection date, then impute as the day of injection date. If this produces a date after the AE end date, assign 01.
 - Otherwise, assign 01.

For partial AE end dates:

- If the year is unknown, then do not impute the date but assign as a missing value. At the time of the analysis, an AE with a complete missing end date will be considered ending at the cut-off date of the analysis in order to derive the duration.
- If the month is unknown, then assign December. If this produces a date after the last contact date, assign this date.
- If the day is unknown, then assign the last day of the month. If this produces a date after the last contact date, assign this date.

7. Study Subjects and Demographics

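### Partial AE start dates are imputed only against the injection date, which for No-treatment controls is 12 weeks after randomisation, so onset and duration of their untreated-period events can be set wrongly

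*SAP*

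**What the plan says.** Section 6.1.7 has three branches for a partial AE start date with a known year, and each is tied to the injection date:

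- Day missing: "If the month and year match the month and year of the injection date, then impute as the day of injection date", stepping back to the 1st if that would fall after the AE end. If the month or year differs, the 1st of the month is used.
- Day and month missing: the start is set to the injection itself when the years agree and any recorded end is later than the injection. Otherwise January is assigned.
- Month missing: "If the year matches the year of injection date and day is on or after day of injection, then assign the month of injection". If the recorded day is earlier than the injection day, the following month is used. Either choice moves back one month, once, if it would fall after the AE end. If the year differs, January is assigned.

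Randomisation is not mentioned, controls have no rule of their own, and the section does not say which injection is meant for a subject treated more than once.

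Section 3.1 gives the timing. RHA subjects "will receive their injection at Visit 1", the visit at which they are randomised. For controls, after the 12-week assessments, "subjects will immediately begin Phase 1b (Visit 1b is on the same day as Visit 5) and will receive their initial treatment with RHA". Section 2.2.2 lists as safety endpoints AEs and "AEs reported from the Common Treatment Response (CTR) diary, from randomization", and section 5 places controls in the Safety population. For Baseline, section 6.1.1 uses "randomization date/time for subjects assigned to control groups", and section 6.1.6.5 uses the same reference for their prior medications.

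**The concern.** The rule suits a subject whose injection marks the start of observation. That is true of the RHA arm. A control is observed untreated for 12 weeks before any injection, so the same rule looks for the onset near the wrong date. A partly dated Phase 1a event can be placed before the subject was randomised, on the day RHA was first given, or after the event had already ended.

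What is at stake is time of onset and duration of AEs in the untreated comparator. Section 6.1.7 applies the convention to derived variables, and its end-date rules name duration as one of them. The comparator is small: at 3:1, 258 / 4 = 64.5, so about 64 controls. The SAP also departs here from its own reference date for controls.

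**Working it through.** The SAP gives no figure on this point, so there is none to reproduce. The check applies the rules literally.

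**Inputs.** From section 3.1: injection on day 0 (RHA) or day 84 (control, 12 × 7). Assumptions: randomisation on any date in 2022–2023, true onset uniform over days 0–83, year always recorded, and January read as 1 January when the day is also missing. All dates were enumerated, with events lasting 3, 7, 14 or 30 days or with no end date.

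**One control: randomised 15 March, injected 7 June (15 March + 84 days).**

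- Day missing, March: the month is not June, so the start is 1 March, before randomisation. The same record in an RHA subject injected on 15 March becomes 15 March.
- Year only, ended 20 April: the end is not after injection, so the start is 1 January. Duration is 31 + 28 + 31 + 20 = 110 days. The longest possible for a Phase 1a onset is 17 + 20 = 37 days.
- Year only, no end date: the start is 7 June, the injection day.
- Day 20, month missing, ended 25 March: 20 June is after the end, so the rule steps back once to 20 May, which is still 56 days after the end.

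**Phase 1a control events overall.** Mean month length is 365 / 12 = 30.4 days.

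- *Day missing, set before randomisation.* Onset falls in the randomisation month, and randomisation is not on the 1st: on average (30.4 − 1) / 2 = 14.7 of the 84 days. 14.7 / 84 = 17.5%, whatever the duration. RHA: 0%.
- *Day missing, set to the injection day.* The injection month also holds 14.7 of the 84 days, so 17.5% is the ceiling, reached with no end date or 30-day events. Shorter events have often ended by then and go to the 1st: 3.3% at 3 days, 7.2% at 7 days, 12.6% at 14 days.
- *Day missing, remainder.* Between 100 − 17.5 − 17.5 = 65% and 100 − 17.5 − 3.3 = 79% stay in Phase 1a.
- *Day and month missing, event over before injection.* The start is 1 January of the onset year. That precedes randomisation unless onset falls in the next calendar year (mean onset day 41.5; 41.5 / 365 = 11.4%) or randomisation was on 1 January (1 / 365 = 0.3%). So 100 − 11.6 ≈ 88% are before randomisation.
- *Day and month missing, no end date.* The injection day applies unless onset and injection fall in different years: 42.5 / 365 = 11.6%. So about 88% go to the injection day and 12% before randomisation.
- *Month missing, event of 3 to 14 days.* After its one step back the rule reaches only about the last month before injection. Onsets earlier than that are (84 − 30.4) / 84 = 63.8%. Of these, onset and injection fall in different years for 54/84 × 57.5/365 = 10.1 percentage points, which go to January. The remaining 63.8 − 10.1 = 53.7% get a start after the event's end. RHA: 0%.
- *Month missing, no end date.* About 86% are set after the injection, 2% on it and 12% before randomisation.

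**No injection date.** For a control who leaves before Visit 1b, none of the comparisons can be evaluated, and the programmer has to decide what applies.

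**Anchored to randomisation.** The control case becomes the RHA case: 0% of day-missing events fall before randomisation, and 0% of 3- to 14-day month-missing events start after they end.

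**The case against.** The strongest reply is that no visible analysis depends on the imputed date to count an event. Section 6.1.7 limits imputation to derived variables, section 9.1 describes every reported AE by SOC and PT, and section 6.1.6.3 identifies device effects from the recorded relationship. The visible AE analysis is descriptive. This stands against the stronger inference a reader might draw, that control events drop out of the untreated period or are counted against RHA. Parts of section 9.1 are redacted, so such an assignment can be neither shown nor excluded. It is a risk only.

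Other points also stand in part:

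- Most day-missing events stay in Phase 1a, and the number of partial dates is unknown.
- The RHA arm is not wholly free of the problem. A year-only event that begins and ends on the injection day fails the test that the end be after injection and goes to January. This is a narrow case.
- Dating an ambiguous control event to the injection day may be called cautious for a device. That does not cover starts before randomisation or after the event's end.
- A reader might add retreatment at Visit 8 to the between-arm argument. It does not belong there: it matters only if the initial injection is the one meant, and it affects both arms.

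None of this answers the core point, that the reference date is the wrong one for controls in Phase 1a.

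**Conclusion.** The point holds as an error in the rule, not as a demonstrated bias in the safety comparison. Followed as written, section 6.1.7 gives some partly dated Phase 1a control events an onset or duration that cannot be right, while the same rule works in the RHA arm apart from the narrow case above. Any imputed date is approximate; the fault here is dates outside the possible period.

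The percentages apply to AEs with partial start dates only and rest on uniform randomisation and onset dates and the assumed durations. The direction does not depend on those assumptions, because it follows from the 12-week gap. The absolute number of affected events cannot be obtained from the SAP and may be small. The primary and co-primary endpoints are not touched. It should be corrected, since the fix is cheap and settles a choice otherwise left to programming.

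**What to change.** In section 6.1.7:

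- Define the reference date as the initial treatment date for RHA subjects and the randomisation date for No-treatment controls, as in sections 6.1.1 and 6.1.6.5. This also covers controls who leave before Visit 1b.
- Use the Visit 1b or retreatment injection date only when the recorded date parts, the end date or other recorded information show onset on or after that injection. The visit of first report should not decide this alone, because Visit 5 and Visit 1b are the same day.
- Do not allow an imputed start before the reference date unless the recorded date parts require it, nor after the AE end date.
- State which injection is meant for retreated subjects.

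The cost is a few lines of SAP text and a small change to the AE derivation code. The drawback is that some ambiguous control events will be dated to the untreated period. A listing, or a sensitivity count with those events placed on the injection day, would show whether that matters.
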